### **Statistical Analysis Plan:**

The baseline and post-intervention observations of the IRLSSG will be calculated using the associated scoring rubric. The distribution of baseline scores will be subtracted from the distribution of post-intervention observations to yield a distribution of difference scores. A Shapiro-Wilk test will be performed on the distribution of difference scores to assess normality. If the assumption of normality is met, parametric paired-samples t-test will be performed to test for significant change in IRLSSG scores. Means and standard deviations will be reported and interpreted for the t-test analysis. If the assumption is violated, then a non-parametric Wilcoxon Signed Rank test will be performed to test for change in IRLSSG scores across time. Medians and interquartile ranges will be reported for the non-parametric test. The PGIC will be scored using its associated scoring rubric. Normality of the two questions from the PGIC will also be tested for using Shapiro-Wilk tests. If the distributions for the questions are normal, means and standard deviations will be reported, and if either or both distributions are non-normal, then medians and interquartile ranges will be reported. All analyses will be conducted using SPSS Version 29 (Armonk, NY: IBM Corp.) and statistical significance will be assumed at an alpha value of 0.05.

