### **Research Methods**

**Study design:** Prospective open-label proof-of-concept trial.

**Study Population**: Subjects must meet all of the enrollment criteria to be eligible for this study. Eligibility criteria may not be waived by the Investigator and are subject to review in the event of a Good Clinical Practice audit and/or health regulatory authority inspection.

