## Participants and protocols:

Participants of both genders will be recruited. Participants with at least a three-month diagnosis of RLS without prior operative intervention will be approached for enrollment in the study. Participants will be enrolled once the trial is described, questions answered, and consent form signed. Pre-treatment IRLSSG scores are collected over the phone on new participant questionnaires. Anyone who does not meet the IRLS criteria for at least mild RLS with a minimum IRLS score of 7 will screen fail. Participants will then have the trial cream described, how to apply it (see below), and then the cream will be mailed to them. Once received, participants will use the cream at least once a night to the affected area(s).

The topical cream will be contained in a jar. The cream will be applied by hand from a measuring spoon and massaged into the skin. The participant will measure 1 teaspoon and apply this amount to each of the regions of the area the participant reports having RLS. Participants will be instructed to apply the topical cream once per day 30-45 minutes before bed for a total duration of two weeks. Participants will be instructed to re-apply the cream if they wake up and feel RLS symptoms.

Participants will receive a follow up phone call at the end of the 2-week study. Post-treatment IRLSSG and the PGIC (patient's global impression of change) will be collected at that time. That completes the study.

Sample Size: 10 participants

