## **Secondary outcome measures:**

1. Patients Global Impression of Change (PGIC)

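### Reporting the PGIC as mean/SD or median/IQR, chosen by a normality test, can fail to show whether anyone got worse; counts at each response level would show it at no cost

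*Protocol*

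**What the plan says.** The Protocol lists one secondary outcome, the PGIC (Secondary outcome measures). It is collected once, at the closing phone call: "Post-treatment IRLSSG and the PGIC (patient's global impression of change) will be collected at that time" (Participants and protocols). The same section sets the size of the study: "Sample Size: 10 participants".

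The Statistical Analysis Plan section deals with the PGIC in three steps:

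- **Scoring.** "The PGIC will be scored using its associated scoring rubric". The rubric is not reproduced, and the number, labels and direction of the response levels are not given.
- **Normality test.** "Normality of the two questions from the PGIC will also be tested for using Shapiro-Wilk tests".
- **Choice of summary.** "If the distributions for the questions are normal, means and standard deviations will be reported, and if either or both distributions are non-normal", the summary becomes median and IQR. Read literally, a non-normal result on one question sets the format for both.

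The Protocol plans no frequency table, no range, and no number improved, unchanged or worse.

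**The concern.** A rating of change is most informative when the reader can see how many participants felt better, how many felt the same and how many felt worse. With at most 10 answers per question, that can be shown in full in one line. The plan instead reduces each question to a centre and a spread, and lets a normality test on those few scores decide which pair of numbers is printed. Scores on a short ordered scale are not normally distributed, so the test answers a question that has little bearing on how best to show them.

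What is at stake is descriptive. The study is uncontrolled, and the PGIC is the only patient-reported outcome besides the restless legs rating scale. If one or two participants felt worse, a reader would want to know, and the planned summary may not say.

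**Working it through.** The Protocol states no calculated figure for the PGIC, so there is nothing to reproduce. The check is whether the planned report can be identical when nobody is worse and when somebody is.

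**Inputs from the Protocol.** Up to 10 answers per question; Shapiro-Wilk; alpha 0.05; mean and SD, or median and IQR.

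**Assumptions.** A 7-level scale with 1 = very much improved, 4 = no change and 5 to 7 = worse. The quartile rule is not stated, so two common ones are used.

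**1. Which answers enter the median and IQR.** Order the answers x1 to x10, from best to worst.

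- Median = (x5 + x6)/2.
- (n+1)p rule: the quartiles sit at positions 11 × 0.25 = 2.75 and 11 × 0.75 = 8.25. They use x2, x3, x8 and x9.
- Linear rule: the quartiles sit at positions 1 + 9 × 0.25 = 3.25 and 1 + 9 × 0.75 = 7.75. They use x3, x4, x7 and x8.

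Under either rule x10, the worst answer, is never used. This holds for any ordered scale.

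**2. A pair in the median/IQR branch.**

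| Answers | Worse | Shapiro-Wilk p | Median | IQR, (n+1)p | IQR, linear |
|---|---|---|---|---|---|
| 1,1,2,2,2,2,3,3,3,3 | 0 | 0.025 | 2 | 1.75–3 | 2–3 |
| 1,1,2,2,2,2,3,3,3,7 | 1 | 0.003 | 2 | 1.75–3 | 2–3 |

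The lower quartile under the first rule is 1 + 0.75 × (2 − 1) = 1.75. Both sets fail the normality test, so this format applies whatever the other question shows. The two reports are identical, although in the second set one participant is very much worse.

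With two participants worse, eight answers of 2 and two of 6 (p < 0.001) give median 2 and an IQR of 2–3 or 2–2. The whole interval lies on the improved side of the scale.

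**3. A pair in the mean/SD branch.** This format applies only if the other question passes the test too.

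- 1,1,1,2,2,3,3,3,4,4 (none worse, p = 0.12): sum 24, sum of squares 70.
- 1,1,2,2,2,2,3,3,3,5 (one worse, p = 0.11): sum 24, sum of squares 70.

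Both have mean 24/10 = 2.4 and SD = √[(70 − 10 × 2.4²)/9] = √(12.4/9) = 1.17.

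**4. How common exact ambiguity is.** There are 8,001 non-constant sets of 10 answers on the assumed scale. Each was put through the rule as a single question, using (n+1)p quartiles.

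| Branch | Distinct possible reports | Reports fitting both none worse and at least one worse |
|---|---|---|
| Median/IQR | 582 | 72 (12%) |
| Mean/SD | 673 | 10 (1.5%) |

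These are shares of possible reports, not probabilities that the trial would produce one. In the mean/SD branch, 528 of the 673 reports leave the exact number worse undetermined, but most of those do not confuse none with some.

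**5. After the change.** Counts at each level recover every answer, so the number worse is always visible.

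**The case against.** The strongest reply is that the harm depends on an instrument the Protocol does not show. If neither question has a separate level for worsening, this reporting rule cannot hide any. That stands, and the point is conditional on it.

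Second, the plan reports a spread as well as a centre, and a wide IQR or a large SD can hint at worsening. That also stands. A reader might infer that the plan routinely conceals deterioration. The enumeration does not support this: exact ambiguity is a minority of possible reports, and rare in the mean/SD branch.

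Third, using one format for both questions is a defensible choice of presentation, and no separate harm from it is shown here. A reader might also want a figure for how often chance decides the branch. None can be given from the Protocol, because it would depend entirely on an assumed pattern of answers.

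Fourth, no hypothesis test, sample size or decision rests on the PGIC, the Protocol does not forbid frequencies, and they could be produced later from the same data. This lowers the severity. It does not remove the point, because the Protocol's own analysis section fixes the summary and the test that selects it; this is not a detail left open for another document.

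**Conclusion.** The point holds as a conditional one of low severity. If a PGIC question is an ordered scale with levels for worsening, the planned summary of up to 10 answers can read the same whether nobody or somebody got worse. The median/IQR branch is the more exposed, because the worst of 10 answers never enters it. The sizes given (72 of 582 and 10 of 673) rest on the assumed 7-level scale, 10 complete answers and (n+1)p quartiles; the first worked pair holds under both quartile rules.

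A reader might infer that the trial's efficacy conclusion is affected. It is not: the PGIC is reported descriptively, and the tests on the rating scale are separate from it.

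**What to change.** In the Statistical Analysis Plan section, keep the sentence on scoring and replace the two sentences on PGIC normality and choice of summary with wording to this effect: for each PGIC question, the number of participants at every response value will be reported, including the numbers improved, unchanged and worse where the scale defines them; if a question is a long numeric scale, a listing or dot plot will be given instead. Drop Shapiro-Wilk for the PGIC. A median may be added.

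State the denominator for each question, since it may fall below 10: a participant with a skin reaction does not continue (Adverse Events).

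Two additions are optional. Exact 95% intervals would be wide (0/10: 0–31%; 1/10: 0.3–44.5%; 2/10: 2.5–55.6%). A listing of each participant's PGIC beside their change on the rating scale would let readers compare the two.

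The cost is two reworded sentences. No new data or calls are needed, and no test or sample size changes.

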## **List of Abbreviations**

RLS, Restless Leg Syndrome; TRPA, transient receptor potential channel of ankyrin; CBDa, Cannabidiolic Acid
